### 13.2. Sensitivity and Supportive Analyses for the Primary Efficacy Variable(s)

As a sensitivity analysis, the analysis of Primary Efficacy Variables will be repeated on two subsets of subjects:

- subjects with no major protocol deviations or protocol exemption
- subjects who are valid completers (ie. subjects who were compliant with the protocol and completed the Double-blind Treatment Period).

If a subset of subjects does not differ from FAS then the analysis will not be repeated for that subset.

### 13.3. Secondary Efficacy Variable Analysis

The secondary efficay endpoints are the following:

- Annual/semiannual decline on disease activity based in the 6-minute walk test (6MWT)
- Modified Medical Research Council Dyspnea Score (MMRC)
- Quality of life (QOL) measured by A Tool to Assess Quality of Life in Idiopathic Pulmonary Fibrosis (ATAQ-IPF)
- Frequency of worsening IPF
- Time to first worsening of IPF

Semiannual rate of change in 6MWT outcome (change in 6MWT distance) will be estimated using the same linear mixed model as for FVC. For estimating the annual rate of change in 6MWT outcomes, the  $t_{ij}$  covariate of this linear mixed model will be modified to measure time in years. For those subjects who were taking MN-001 during the DBT phase and OLE phase as well, semiannual rate of change will be estimated for the DBT and OLE phases as a whole. For those subjects who were taking Placebo during the DBT phase and MN-001 during the OLE phase, semiannual rate of change will be estimated for the DBT phase and for the OLE phase respectively.

Descriptive statistics of estimated semiannual and annual 6MWT measurements will be provided by treatment arm and visit. Descriptive statistics will be provided of actual MMRC scores and ATAQ-IPF total scores as well as changes from baseline of these scores, by treatment arm and visit.

Number of events related to worsening IPF will be calculated by treatment arm and event category (acute IPF exacerbation, hospitalization due to respiratory symptoms, IPF related fatal events, lung transplantation). Number and proportion of subjects in different event categories will also be provided: a subject may be counted multiple times, but within each category will be counted only once.

For time to first worsening in IPF a Kaplan-Meier analysis will be performed, estimating the mean and median time to first worsening (and their 95% CI) for each treatment arm. Those subjects who do not experience any adverse event related to worsening in IPF until Month 6 will be censored at their last visit. The estimated survival functions will be presented graphically.

Protocol Short Title: A Study of MN-001 in Subjects with

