#### 10.1. Definition of Treatment Arms

Treatment arms will be denoted as follows in the TLFs:

- "MN-001" 750 mg of MN-001 administered orally twice daily
- "Placebo" Matching Placebo administered orally twice daily
- "Former Placebo" Matching Placebo administered orally twice daily during the Double-Blind Treatment Phase and 750 mg of MN-001 administered orally twice daily during the OLE Phase

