### **10.2.** Definition of Study Phases

Double Blind Treatment Phase (DBT Phase)

The DBT Phase starts with Visit 3 which is the Day 1 of the DBT phase.

The DBT Phase ends with end of the day of Visit 8 (Month 6) and assessments taken on this visit will be considered as belonging to the DBT phase.

Open Label Extension Phase (OLE Phase)

The OLE Phase starts on the following day of Visit 8 and ends with Visit 14(Month 13).

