### 13.1. Primary Efficacy Variable Analysis(s)

The primary efficacy endpoints are the absolute and relative change from baseline in FVC and FVC% predicted up to 26 weeks, and the semiannual decline of disease activity based on FVC. To estimate the semiannualized rate of change in FVC between baseline and Month 6, a random intercept, random slope linear mixed model will be fitted (using proc mixed in SAS). Missing data will not be imputed because the ML-estimate is unbiased for this model in case of a Missing at Random (MAR) mechanism.

The model equation is the following:

$$Y_{ij} = \alpha + \beta_1 t_{ij} x_{1i} + \beta_2 t_{ij} x_{2i} + a_i + b_i t_{ij} + \varepsilon_{ij}$$

where:

 $Y_{ij}$  is the FVC value for the  $\mathrm{i}^{\mathrm{th}}$  subject at the  $\mathrm{j}^{\mathrm{th}}$  time point

 $\alpha$  is the common intercept

 $t_{ij}$  denotes time point j for the ith subject (actual time in half-years)

 $x_{1i}$  = 1 if subject *i* is in the active treatment arm, and 0 otherwise

 $x_{2i}$  = 1 if the subject *i* is in the placebo arm, and 0 otherwise

 $a_i$  and  $b_i$  are random effects (random intercepts and slopes) for subject i

Statistical Analysis Plan v1.0

Protocol Short Title: A Study of MN-001 in Subjects with

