### 13.4. Sensitivity and Supportive Analyses for the Secondary Efficacy Variable(s)

For those subset of subjects who were compliant with the protocol and completed the DBT and OLE Phases, the analysis of 6MWT will be repeated. If this subset of subjects does not differ from FAS then the analysis will not be repeated.

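### SAP 13.3 fits the semiannual 6MWT slope over 12 months on MN-001 but over 6 months on placebo, and leaves unclear whether a like-for-like contrast over the randomised period is intended

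*SAP*

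**What the plan says.** SAP 13.3 makes three statements about the 6MWT slope.

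- The semiannual rate "will be estimated using the same linear mixed model as for FVC". The FVC model in SAP 13.1 is introduced with "To estimate the semiannualized rate of change in FVC between baseline and Month 6", has one slope per arm, and carries the null hypothesis beta1 = beta2.
- For subjects on MN-001 in both phases, the "semiannual rate of change will be estimated for the DBT and OLE phases as a whole".
- For subjects who moved from placebo to MN-001, the "semiannual rate of change will be estimated for the DBT phase and for the OLE phase respectively".

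SAP 10.2 fixes the boundary: "The DBT Phase ends with end of the day of Visit 8 (Month 6"). The protocol's visit schedule has 6MWT at baseline (Visit 2) and Months 3, 6, 9 and 12. The MN-001 slope thus uses five time points over 12 months, and the slope on placebo uses three over 6 months.

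SAP 10.1 separates Placebo from Former Placebo, the latter defined as "Matching Placebo administered orally twice daily during the Double-Blind Treatment Phase" followed by MN-001 in the extension. MN-001 has one label for both phases.

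The SAP 13.4 repeat is for compliant subjects who "completed the DBT and OLE Phases, the analysis of 6MWT will be repeated". The matching FVC subset in SAP 13.2 is "subjects who were compliant with the protocol and completed the Double-blind Treatment Period".

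On the rate itself, protocol Section 5.2 names only the semiannual decline, while the protocol synopsis and Section 10 list both annual and semiannual decline. SAP 13.3 obtains the annual rate by rescaling time to years and gives no window for it.

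**The concern.** Only baseline to Month 6 is randomised and blinded. In months 6 to 12 every continuing subject takes open-label MN-001. A 12-month MN-001 slope beside a 6-month placebo slope therefore mixes treatment with calendar period and open-label status.

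The two window sentences are the more specific instruction, and they do not list a months 0–6 slope for MN-001. Read literally, they also cover only subjects who entered the extension, so they give no window for anyone who stopped earlier, although efficacy is to be analysed in the FAS. A programmer has to choose between these sentences and the cross-reference to the FVC model.

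At stake is the 6MWT slope difference that this pilot would hand to later study design. FVC has Month 3 and Month 6 ANCOVAs as well as its slope test; 6MWT has no ANCOVA, and no 6MWT slope test is restated.

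**Working it through.** The plan states no 6MWT effect, SD or expected course, so there is no figure to reproduce. The check asks what the two windows yield when the arms truly follow the same course.

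**Inputs from the documents.** 6MWT times; about 15 subjects at 2:1, taken as 10 and 5; the SAP 13.1 model; time in half-years = days × 2/365.25. This gives 182 × 2/365.25 = 0.997 at 26 weeks and 364 × 2/365.25 = 1.993 at 52 weeks, treated as 1 and 2.

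**Step 1, closed form.** Let both arms decline at s1 per half-year in months 0–6 and s2 in months 6–12. The MN-001 times are 0, 0.5, 1, 1.5, 2 (mean 1, Sxx = 2.5), with expected values 0, s1/2, s1, s1 + s2/2, s1 + s2.

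- Sum of deviation × value = −0.5(s1/2) + 0.5(s1 + s2/2) + (s1 + s2) = 1.25(s1 + s2).
- MN-001 least-squares slope = 1.25(s1 + s2)/2.5 = (s1 + s2)/2.
- Placebo slope over 0, 0.5, 1 = s1.
- Apparent difference = (s1 + s2)/2 − s1 = **(s2 − s1)/2**, which is zero when s2 = s1.

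**Step 2, the SAP model.** Generalised least squares with a common intercept, two arm slopes, and random intercept and slope. Assumed, not from the documents: s1 = −20 m per half-year and five sets of SDs (intercept/slope/residual, uncorrelated). As written means five time points on MN-001 and three on placebo; changed means three in both arms. Results are in m per half-year, for s2 = 0 unless stated. Signs of the difference reverse for s2 = −40, and from s2 = −10 to s2 = −30.

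| SDs | False difference as written | SE as written | SE changed | SE increase | RMSE as written, s2 = 0 or −40 | RMSE as written, s2 = −10 or −30 |
|---|---|---|---|---|---|---|
| 100/20/30 | 9.73 | 22.39 | 25.25 | 12.7% | 24.4 | 22.9 |
| 100/40/30 | 9.73 | 29.35 | 31.58 | 7.6% | 30.9 | 29.8 |
| 100/40/20 | 9.88 | 25.55 | 26.75 | 4.7% | 27.4 | 26.0 |
| 100/30/40 | 9.54 | 30.50 | 34.09 | 11.8% | 32.0 | 30.9 |
| 80/20/20 | 9.81 | 17.07 | 18.78 | 10.0% | 19.7 | 17.8 |

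- The false difference is 0.31 (9.54/30.50) to 0.57 (9.81/17.07) of its SE.
- At s2 = −10 or −30 it is 4.77 to 4.94 in size. At s2 = −20 it is 0.
- With months 0–6 in both arms it is 0 throughout, so the RMSE after the change equals the changed SE.
- RMSE is lower as written in 3 of 5 sets in the larger cases (all but the third and fifth) and in all 5 in the milder cases.

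**Step 3, separate fits.** Fitting each arm on its own gives exactly ±10.00 in the larger cases, with SEs of 17.20 to 31.21 as written (0.32–0.58 SE) and an SE increase of 4.8–13.1%. The result does not depend on a joint fit.

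**The case against.** The strongest reply is that the like-for-like fit is already there. The opening sentence imports a model that covers baseline to Month 6 in both arms and tests beta1 = beta2. That model has only two slopes, so it cannot also hold a whole-period MN-001 slope, a placebo slope and a former-placebo extension slope. One can coherently read the first sentence as the randomised comparison and the later ones as extra estimates by exposure. This stands as a possible reading, and a reader who infers that no such contrast is planned goes further than the text allows. It does not settle the matter: the later sentences are the ones that set windows, and nothing says they are additional.

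Nor does SAP 13.3 tell anyone to subtract one slope from the other. The stated output is descriptive, so harm arises only if the two slopes are compared. With about 15 subjects and all efficacy measurements listed, a months 0–6 contrast could be refitted later. Both points stand and limit the severity.

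Three other inferences should be avoided.

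- A reader might take the annual rate to be a SAP addition. It is not: the protocol synopsis and Section 10 already list it, which gives some reason to use 12-month data where exposure is continuous. The gap is the unstated window.
- A reader might say SAP 13.4 itself imposes the mismatch. It selects subjects, not time windows.
- A reader might expect the change to improve accuracy. The RMSE figures do not support that.

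**Conclusion.** The concern holds as a minor one. SAP 13.3 sets different windows by arm for the semiannual 6MWT slope, conflicts with its own cross-reference to the FVC model, and does not make clear that a modelled contrast over the randomised period will be produced.

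If the reported slopes are compared, the bias is about (s2 − s1)/2. It is nil under linear decline over 12 months, about ±5 m per half-year for milder changes, and up to about ±10 m (0.31–0.58 SE) if decline stops or doubles after Month 6. These sizes rest on assumed slopes and SDs, since the documents give none.

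The documents do not support a claim about type I error: SAP 10.6 treats P values descriptively and 6MWT is secondary. By-visit summaries and listings remain available, so what is at risk is the modelled slope contrast. FVC, MMRC and ATAQ-IPF are not affected.

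**What to change.** In SAP 13.3, state that the between-arm 6MWT slope contrast (beta1 − beta2, with 95% CI) uses baseline, Month 3 and Month 6 data in both arms, in the FAS. Report the 12-month MN-001 slope and the former-placebo extension slope separately, labelled descriptive. State the window for the annual rate, and label any placebo annual rate an extrapolation from 6 months. For this contrast, base the SAP 13.4 repeat on completers of the double-blind phase, as SAP 13.2 does for FVC.

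The cost is SAP wording and one extra model fit, with no new data. The SE of the slope difference rises by about 5–13%. What is gained is an unbiased, interpretable randomised contrast. No planned output is lost.

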8.8.2.11. Worsening IPF

Worsening IPF is defined as acute IPF exacerbation, hospitalization due to respiratory symptoms, IPF related fatal events, or lung transplantation.

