#### 6. STUDY METHODS

### 6.1. Overall Study Design and Plan

This is a randomized, placebo-controlled, double-blind 6-month study followed by a 6-month open-label extension phase to evaluate the efficacy, safety, and tolerability of MN-001 in moderate to severe IPF patients. MN-001 750 mg or matching Placebo will be orally administered twice daily over a 26-week period in subjects with a confirmed diagnosis of moderate to severe IPF per the ATS 2011 Guidelines (Raghu et al, 2011).

Approximately 15 subjects are planned to be enrolled. This study will consist of two treatment arms, MN-001 and matching Placebo. Randomization will occur in a 2:1 ratio (MN-001:Placebo). Eligible subjects will consist of males and females ranging in age from 21 to 80 years old, inclusive. The study will consist of a Screening Phase (up to 3 months prior to Day 1) followed by a 26-week double-blind Treatment Phase, a 26 week Open-Label Extension (OLE) phase and a Follow-up Visit (within 4 weeks after the last dose).

Overall study design and plan is described in detail in Final Protocol Amendment 1, Section 6. Overall Study Design and plan: Description.

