#### 8. SAMPLE SIZE DETERMINATION

No prior data are available on which to base assumptions for sample size/power considerations. The results of this pilot study will be used to design future studies, and the sample size of approximately 15 subjects is deemed to be appropriate for this purpose.

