### 10.8. Analysis Software

All analysis will be performed using SAS® Software version 9.4 or above.

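### The Kaplan-Meier mean time to first worsening has no common time limit, so the two arms' means may not be comparable, and no rule covers an unreached median or an arm without events

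*SAP*

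**What the plan says.** SAP section 13.3 specifies a Kaplan-Meier analysis of time to first worsening, "estimating the mean and median time to first worsening (and their 95% CI) for each treatment arm". The censoring rule is: "Those subjects who do not experience any adverse event related to worsening in IPF until Month 6 will be censored at their last visit". Survival curves and a two-sided 0.05 log-rank test accompany the estimates. The section gives no upper time limit for the mean, no rule for a median that is not reached, and no rule for an arm without events.

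On software, SAP section 10.8 says only: "All analysis will be performed using SAS® Software version 9.4 or above". No procedure or option is named for the Kaplan-Meier analysis, although section 13.1 does name one for the FVC model.

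The setting is as follows.
- **Follow-up:** the design is screening "followed by a 26-week double-blind Treatment Phase, a 26 week Open-Label Extension (OLE) phase" (SAP 6.1). The Month 6 visit has a window of ±5 days (schedule of events in both documents).
- **Size:** "the sample size of approximately 15 subjects is deemed to be appropriate for this purpose" (SAP 8), randomized 2:1.
- **Event:** "Worsening IPF is defined as acute IPF exacerbation, hospitalization due to respiratory symptoms, IPF related fatal events, or lung transplantation" (Protocol 8.8.2.11).
- **Event rate:** none is given in either document.

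**The concern.** A Kaplan-Meier mean is the area under the survival curve. If the longest time in an arm is censored, the curve does not fall to zero and the area has no defined end, so a cut must be chosen. If each arm is cut at a different time, the two means describe different periods. An arm with a single early event would then show a short mean even if every other subject stayed event-free to Month 6, and an arm with no events would have no mean at all.

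At stake is the numerical summary of this endpoint. The SAP reads its P values descriptively (section 10.6) and uses the pilot to design later studies (section 8), so the estimates carry most of the weight. The separate frequency endpoint counts subjects by event category, and one subject may appear in several. It therefore does not give the number per arm with any worsening.

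**Working it through.** The plan states no figure for this endpoint, so there is nothing to reproduce.

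**Inputs.** From the documents: about 15 subjects at 2:1, giving 15 × 2/3 = 10 on MN-001 and 5 on placebo; 26 weeks × 7 = 182 days. Assumed, because the documents are silent: the 26-week event risk, the dropout rate and the convention for cutting the mean.

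**1. Invented data: the cut can reverse the direction.** MN-001 has 1 event in 10 (day 60). Placebo has 2 in 5 (days 60 and 150). All others are censored at day 182.
- Cut at each arm's last event: MN-001 60 × 1 = 60.0 days; placebo 60 + 0.8 × 90 = 132.0 days. This favours placebo.
- Cut at day 182 in both arms: MN-001 60 + 0.9 × 122 = 169.8 days; placebo 132 + 0.6 × 32 = 151.2 days. This favours MN-001.
- Cut at each arm's last observation: again 169.8 and 151.2, because both arms end at day 182.

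**2. How often the median is reached.** Without dropout, the curve falls to 50% with at least 5 events in 10 or 3 in 5 (binomial tail probabilities, same risk in both arms).

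| 26-week risk | MN-001 (n=10) | Placebo (n=5) |
|---|---|---|
| 10% | 0.002 | 0.009 |
| 20% | 0.033 | 0.058 |
| 30% | 0.150 | 0.163 |
| 40% | 0.367 | 0.317 |
| 50% | 0.623 | 0.500 |

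Dropout raises these a little: with 15% dropout and 20% risk, the simulated placebo figure is 0.086.

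**3. How often an arm has no events.** With q = 1 − risk, the same in both arms and no dropout, the chance that at least one arm has none is 1 − (1 − q^10)(1 − q^5).
- 10% risk: 1 − 0.651 × 0.410 = 73%
- 15% risk: 1 − 0.803 × 0.556 = 55%
- 20% risk: 1 − 0.893 × 0.672 = 40%

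**4. How often the cut changes the sign.** Simulation of 10 v 5 subjects with exponential times and the Month 6 visit at 182 ± 5 days. Placebo risk was 10, 20, 30, 40 or 60%, halved on MN-001, with dropout of 0 or 15% and 6,000 runs per scenario. The common cut was day 177.
- **Last-event cut, trials with events in both arms:** opposite sign to the common-cut difference in 27-34%. The two cut times differ by a median of 41-52 days. This mean favours placebo in 34-48%, against 16-28% for the common-cut mean in the same trials.
- **Last-event cut, as a share of all trials:** from 0.288 × (1 − 0.861) = 4% (10%/5% risk, 15% dropout) to 0.286 × (1 − 0.034) = 28% (60%/30% risk, no dropout).
- **Last-observation cut, all trials:** opposite sign in 1-2%.

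**The case against.** A reader might infer that the planned mean will be cut at a different time in each arm and so is likely to mislead. The documents do not support that. They name the software but no convention, and a last-observation cut ends both arms close to Month 6 and rarely changes the sign.

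A reader might also infer that most subjects will be event-free at Month 6 and the median will not be reached. That is plausible for subjects required to be in stable condition at entry (Protocol 7.2.1), but it is not documented. The SAP describes the disease as moderate to severe, and any hospitalization for respiratory symptoms counts as an event.

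Three further objections have force.
- Part of the instability comes from having 15 subjects: even a common-cut mean favours placebo in 16-28% of simulated trials with events in both arms where MN-001 halves the risk.
- The means will not be read alone. Curves, counts by event category and a log-rank test are planned, and all efficacy measurements are listed.
- A restricted mean has its own weakness: in an arm with no events it equals the cut time with zero estimated standard error.

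These points limit the importance and shape the fix. They do not remove the gap: the SAP promises an estimate with a CI that, under its own censoring rule, is undefined whenever an arm's longest time is censored.

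**Conclusion.** The point holds as a gap in specification. Without a common restriction time, the planned mean is not identified in an arm whose longest time is censored. How far this matters depends on the convention used: the sign differs from a common-cut comparison in about 27-34% of trials with events in both arms under a last-event cut, and in 1-2% of trials under a last-observation cut. Without dropout, the median is reached in at most about 6% of trials per arm at 10-20% risk, but in about 32-62% at 40-50%.

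These figures rest on assumed event risks, exponential times and a 10 v 5 split. Importance is minor to moderate: the endpoint is secondary and descriptive in a pilot, and the curves and log-rank test do not depend on the mean.

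**What to change.** In SAP section 13.3:
1. Replace the unrestricted mean by the restricted mean event-free time to one common time in both arms: 182 days, or the shorter of the two arms' longest follow-up if the ±5-day Month 6 window makes that earlier. Report the between-arm difference with its 95% CI.
2. Add event-free n/N at Month 6 per arm with an exact 95% CI, and state how subjects censored before Month 6 count in N. Make this the main summary when an arm has no events. The exact interval still conveys uncertainty there: for 5 of 5 event-free, the lower limit is 0.025^(1/5) = 0.48.
3. Report the median as not reached where that applies.
4. Censor event-free subjects at their last visit up to Month 6, since the present wording could also be read as a later open-label visit.

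The cost is a few SAP sentences and a few more lines of analysis, with no new data. The remaining drawback is that the restricted-mean CI is unreliable when an arm has no events, which is why item 2 is needed. The change should be made before unblinding, the point by which SAP section 3 requires final approval.

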6.4. Follow-up Phase

All subjects who complete the study will return for their final visit at 4 weeks after their last dose for safety assessments and to assess adverse event status and document concomitant medications.

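### SAP 13.3 checks for a first IPF worsening only to Month 6 but censors at the last visit with no phase limit, which read literally is Month 13 for completers

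*SAP*

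**What the plan says.** SAP 13.3 plans a Kaplan-Meier analysis of time to first worsening, with mean, median and confidence intervals per arm, a plot of the curves, and a two-sided log-rank test at 0.05. The only censoring rule is: "Those subjects who do not experience any adverse event related to worsening in IPF until Month 6 will be censored at their last visit". No truncation time is given for the mean.

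SAP 10.2 ends the double-blind phase at Visit 8 (Month 6). Of the next phase it says: "The OLE Phase starts on the following day of Visit 8 and ends with Visit 14(Month 13". Protocol 6.4 agrees on the last contact: "All subjects who complete the study will return for their final visit at 4 weeks after their last dose". Protocol 8.8.1.4 places that visit at Month 13.

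Under Protocol 6.3, placebo subjects receive MN-001 after Month 6 and MN-001 subjects stay on it. Protocol 8.8.2.12 records adverse events until participation ends, so a worsening after Month 6 would be in the database. The worsening definition (Protocol 8.8.2.11, SAP 5.2.2) carries no time window, and SAP 15 does not mention this endpoint.

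**The concern.** Censoring a subject at time t states that the subject was under observation and event-free up to t. The SAP sentence establishes event-free status only to Month 6, yet allows t to be as late as Month 13. A first worsening in between is then neither counted as an event nor used to end the event-free time, so the curve is flat after Month 6 by construction. For the placebo arm, that stretch is also time on active drug.

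Time to first worsening is a named secondary objective, and SAP 8 says the pilot will be used to design future studies. A curve that appears to show no worsening for seven months could be carried into that planning.

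**Working it through.** **1. The last visit of a completer.** Double-blind 26 weeks + open-label 26 weeks + follow-up 4 weeks = week 56, the Month 13 visit. The two documents agree.

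**2. The rule applied to one subject.** Take a completer whose first non-fatal worsening is at Month 8.
- Literal reading: no event by Month 6, so censored at Month 13. The curve shows event-free time from Month 8 to Month 13 that did not occur.
- Double-blind reading: censored at Visit 8. Correct for the period it covers.

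**3. Possible size of the tail error.** The documents give no worsening rate, so the risks here are assumptions: 6-month risk p of 10%, 20% or 40%, constant hazard, the same in both arms and phases, 15 subjects, non-fatal events, no dropout.

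Hazard per month L = -ln(1-p)/6, and S(t) = (1-p)^(t/6). The literal curve shows S(6) at Month 13; the actual event-free proportion is S(13). First events left out = 15 × [S(6) - S(13)].

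| p | Shown at Month 13, S(6) | Actual, S(13) | First events left out, of 15 | Shown at risk just after Month 6, 15 × S(6) |
|---|---|---|---|---|
| 10% | 0.900 | 0.796 | 1.56 | 13.5 |
| 20% | 0.800 | 0.617 | 2.75 | 12.0 |
| 40% | 0.600 | 0.331 | 4.04 | 9.0 |

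With 30% dropout by Month 13, independent of worsening: m = -ln(0.7)/13, k = L + m, and events left out = 15 × (L/k) × (e^(-6k) - e^(-13k)) = 1.21, 2.13 or 3.15.

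**4. The mean, on one horizon.** To Month 13, the literal rule gives (1 - S(6))/L + 7 × S(6). Counting every first event gives (1 - S(13))/L.

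| p | Literal, months | All first events counted, months | Overstatement, months |
|---|---|---|---|
| 10% | 5.69 + 6.30 = 11.99 | 11.62 | 0.37 |
| 20% | 5.38 + 5.60 = 10.98 | 10.31 | 0.67 |
| 40% | 4.70 + 4.20 = 8.90 | 7.86 | 1.04 |

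This applies only if the mean is integrated to the last observation. If it is integrated to the last event, the literal rule and a Month 6 cut-off give the same value.

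**5. The log-rank test.** Under both rules the only events counted are those up to Month 6. At each such event time, a subject still in follow-up is in the risk set whether later censored at Month 6 or at Month 13. Observed, expected and variance terms are therefore identical. In 20,000 simulated trials (10 versus 5 subjects, with dropout), 19,679 gave a computable statistic and the largest chi-square difference was 0. The curve to Month 6, and any median reached by then, are unchanged for the same reason. This treats Month 6 as one date. With actual Visit 8 dates (±5 days), only an event inside that window could alter a risk set.

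**The case against.** The strongest reply is that the sentence contains its own window. The SAP uses Month 6 elsewhere to mark the double-blind period: SAP 13.1 estimates the FVC slope between baseline and Month 6, and SAP 10.2 ends the phase there. SAP 10.1 also keeps a separate label, Former Placebo, for subjects given "Matching Placebo administered orally twice daily during the Double-Blind Treatment Phase and 750 mg of MN-001", so a curve labelled Placebo should not run into the open-label phase. On that view, the last visit plainly means the last double-blind visit.

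This stands as evidence of intent. It does not settle the text. Where SAP 13.2 means the double-blind phase it says so ("subjects who were compliant with the protocol and completed the Double-blind Treatment Period"), SAP 13.4 names both phases, and the censoring sentence names none. A programmer following it would use Month 13.

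Three further objections also stand:
- The tail is numerically wrong only if a first worsening actually follows Month 6. Without one, the remaining fault is that the placebo tail is time on MN-001.
- A subject withdrawn soon after a late worsening would be censored near the event, not at Month 13.
- Late events are missing from the curve only. SAP 13 lists all efficacy measurements, and SAP 14.1 reports adverse events by phase and lists serious events and deaths.

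**Conclusion.** The rule is wrong as written, although the intent was probably sound. It joins an event check that stops at Month 6 to a censoring date that, for completers, is Month 13. The effect is limited to the tail, the numbers at risk after Month 6 and, under one convention, the mean, which would be overstated by about 0.4 to 1.0 months on a 13-month horizon. That range rests on the assumed risks of 10% to 40%, constant hazard and no dropout.

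A reader might infer that open-label time contaminates the treatment comparison. The documents do not support this, because events after Month 6 do not enter the log-rank test under the stated rule. A reader might also set a mean taken to Month 13 beside one taken to Month 6 and see a large inflation. Most of that gap is the longer horizon.

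Severity is minor: a secondary endpoint in about 15 subjects, with P values interpreted descriptively (SAP 10.6). No primary result is touched.

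**What to change.** In SAP 13.3, state that:
- first worsening events count if their onset is from Day 1 through Visit 8;
- event-free subjects are censored at their last visit on or before Visit 8 (Month 6);
- the Kaplan-Meier mean is restricted, in both arms, to one common time no later than Month 6.

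If the sponsor wants the open-label phase included, present it as a separate display that counts events to the last visit and states how the placebo subjects' switch to MN-001 is handled.

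The cost is a few sentences in SAP 13.3 and one censoring-date derivation, with no new data. It should be settled before the treatment codes are unblinded, the point by which SAP 3 requires final approval.
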